4.3 Sample Size

Assuming 4% of subjects do not achieve SVR₁₂ and assuming the 5-year event rate of the composite clinical outcome is 20% in the non-SVR₁₂ subjects, with a 75% reduction in SVR₁₂ subjects (Hazard Ratio of 0.25),^{1,2} then based on two-sample log rank test (using EAST 6.0), a sample size of at least 2000 subjects enrolled in TOPAZ-I (planned to enroll 1650 subjects) and TOPAZ II (planned to enroll 600 subjects) provides greater than 80% power to reject the null hypothesis of no difference between SVR₁₂ and non-SVR₁₂

subjects in the rate of clinical outcome events. Power calculations were based on a dropout rate of up to 20% for the hazard ratio.

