6.3 Missing Data Imputation

No data will be imputed for any efficacy or safety analyses except for the PRO questionnaires, for analyses of the HCV RNA endpoints, and for analysis of the persistence of resistance. If a respondent answers at least 50% of the items in a multi-item scale of the SF-36v2, the missing items will be imputed with the average score of the answered items in the same scale. In cases where the respondent did not answer at least 50% of the items, the score for that domain will be considered missing. Similarly, the missing items of the FACIT-F questionnaire will be imputed with the average score of the answered items in the same scale as long as more than 50% (≥ 7 out of 13) of the items in the scale are answered. The SF-36v2 Mental and Physical Component Summary measures will not be computed if any domain is missing.

HCV RNA values will be selected for an SVR analysis based on visit windows as defined in Section 6.2. When there is no HCV RNA value in a visit window based on defined visit windows, the closest values before and after the window, regardless of the value chosen for the subsequent and preceding window, will be used for the flanking imputation described below.

If a subject has a missing HCV RNA value at a post-Day 1 visit but with undetectable or unquantifiable HCV RNA levels at both the preceding value and succeeding value, the HCV RNA level will be considered undetectable or unquantifiable, respectively, at this visit for this subject. In addition, if a subject has an unquantifiable HCV RNA level at the preceding value and an undetectable HCV RNA level at the succeeding value, or vice versa, the HCV RNA level will be imputed as unquantifiable at this visit for this subject. For SVR analysis, if there is no value in the appropriate window after flanking imputation but there is an HCV RNA value after the window, then it will be imputed into the SVR window. Subsequent to this flanking imputation, if a subject is missing a value for the visit window associated with the analysis, the subject will be imputed as a visit failure (i.e., not undetectable or unquantifiable).

If a subject starts another treatment for HCV, then all HCV RNA values for this subject measured on or after the start date of the new HCV treatment will be excluded from analyses. The subject will be considered a failure for summaries of viral response at all time points after the start of the new HCV treatment.

HCV RNA < LLOQ Analyses for SVR

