If a subject is missing an HCV RNA value for the visit window associated with the analysis of SVR after performing the imputations described above, then this value will be imputed with an HCV RNA value from a local laboratory if present; otherwise, the HCV RNA value for this visit will be missing. Subjects with missing HCV RNA data in the analysis window, after imputations, will be imputed as a failure.

HCV RNA Analyses for Relapse and Virologic Failure

If HCV RNA values from the central laboratory are missing but a local laboratory value is present in the appropriate time period, then the local laboratory value will be used to assess post-treatment relapse and on-treatment virologic failure.

Finally, missing sequence data will be imputed as follows in the analysis of the persistence of resistance from the sequences from PT Week 52 through PT Week 260 (5 years). If a signature variant is not detectable by population, clonal or deep sequencing at PT Week 24 (or later), the variant is imputed as not detectable at the PT Week 52 (or timepoints after the sequence with the variant not detectable) and time points thereafter if a sample from Post-Treatment Week 52 or later is not sequenced. If a signature variant is detectable by population, clonal, or deep sequencing at Post-Treatment Week 52 or later, then the variant is imputed as being detectable at earlier time points if the sample at the earlier time point is not sequenced.

7.0 Demographics, Baseline Characteristics, Medical History, and Previous/Concomitant Medications

Demographics, baseline characteristics, medical history, and previous/concomitant medications will be summarized overall and by presence of cirrhosis and genotype 1 subtype on the safety population.

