For relapse analyses, the completion of treatment is defined as a study drug duration \geq 77 days for subjects assigned to 12 weeks of treatment and \geq 154 days for subjects assigned to 24 weeks of treatment. If the last available post treatment value is \geq LLOQ,

then the subject will be considered a relapse (i.e., will not require confirmation). Relapse analyses will exclude subjects who do not have any post-treatment HCV RNA values.

Reasons for SVR₁₂ Non-Response

Subjects who do not achieve SVR₁₂ (SVR₁₂ non-responders) will be categorized as having:

1. On-treatment virologic failure (see **On-treatment virologic failure** definition);
2. Relapse (defined according to the **Relapse₁₂** definition for subjects who complete treatment);
3. Prematurely discontinued study drug with no on-treatment virologic failure (defined as any SVR₁₂ non-responder who prematurely discontinued study drug (duration < 77 days for subjects assigned to 12 weeks of treatment or duration < 154 days for subjects assigned to 24 weeks of treatment) and did not meet the **On-treatment virologic failure definition**);
4. Missing follow-up data in the SVR₁₂ window (defined as any subject who completed study drug without data in the SVR₁₂ window and not meeting the definitions of [1], [2], or [3]);
5. Other (defined as any SVR₁₂ non-responder not meeting the definitions of [1] – [4], such as a subject with a single quantifiable value within the SVR₁₂ window followed by an undetectable value beyond the SVR₁₂ window).

Reasons for SVR₂₄ Non-Response

Subjects who do not achieve SVR₂₄ (SVR₂₄ non-responders) will be categorized as having:

1. On-treatment virologic failure (see **On-treatment virologic failure** definition);
2. Relapse (defined according to the **Relapse₁₂** definition for subjects who complete treatment);

3. Relapsed after achieving SVR₁₂ (see **Relapse₂₄**);
4. Prematurely discontinued study drug with no on-treatment virologic failure (defined as any SVR₂₄ non-responder who prematurely discontinued study drug and did not meet the **On-treatment virologic failure, Relapse₁₂, or Relapse₂₄** definitions);
5. Missing follow-up data in the SVR₂₄ window (defined as any subject who completed study drug without data in the SVR₂₄ window, and not meeting the definitions of [1], [2], [3], or [4]);
6. Other (defined as any SVR₂₄ non-responder not meeting the definitions of [1] – [5]).

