10.3 Primary Efficacy Analysis

The primary efficacy analysis will be conducted among subjects in the ITT population as described in Section 5.1. HCV RNA values and SVR₁₂ will be imputed as described in Section 6.3.

The primary efficacy endpoint is to assess the effect of response to treatment (as assessed by SVR₁₂ status) on clinical outcomes by comparing the time to incidence of the following events between subjects who achieve SVR₁₂ and those who do not.

- All-cause death
- Liver-related death
- Liver decompensation
- Liver transplantation
- Hepatocellular carcinoma

- Composite of any of the above outcomes

For each of the six event types as listed above, a subject's time to event will be defined as the number of days from the first day of study drug dosing for the subject to the day the subject experiences an event of interest. All events of interest will be included, regardless of whether the event occurred while the subject is still taking study drug or has previously discontinued study drug. If the subject does not experience an event of interest nor has the subject died (all-cause death), the subject's data will be censored at the date of the subject's last available assessment of clinical outcomes. For subjects with no post-baseline assessment, the subject's data will be censored on the first day of study drug dosing. All-cause death is a censoring event for liver-related death, liver decompensation, liver transplantation and hepatocellular carcinoma. Time to the composite of clinical outcomes is the time to the first occurrence of any clinical outcome.

For each of the six event types, the distribution of time to event will be estimated for subjects who have achieved SVR₁₂ and those who haven't using Kaplan-Meier methodology and compared between the subjects who have achieved SVR₁₂ and those who haven't using the log-rank test.

For each of the six event types, the 1-, 2-, 3-, 4-, and 5-year event-free survival rate will be estimated using Kaplan-Meier methodology and a 95% confidence interval will be constructed separately for those who have achieved SVR₁₂ and those who have not. For each of the six event types, a Cox proportional hazards (PH) model will be constructed to include all the baseline characteristics as described in Section 7.1, SVR₁₂ status, and other variables as appropriate.

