10.6 Sensitivity Analysis for the Efficacy Endpoint of SVR₁₂

In addition to presenting the secondary efficacy endpoint of SVR₁₂ as described in Section 10.4, two sensitivity analyses of SVR₁₂ will be presented using the following modified populations. The first sensitivity analysis of SVR₁₂ will be conducted using a Modified Intent-to-Treat Genotype (mITT-GT) population that includes subjects who receive at least 1 dose of study drug (with imputation as described in Section 6.3) but excludes the subjects who are not of HCV genotype 1 infection. The mITT-GT population is used to reduce the risk of bias that could occur due to enrolled population deviating from the protocol selected study population.

The other sensitivity analysis of SVR₁₂ will be conducted using a Modified Intent-to-Treat Genotype and Virologic Failure (mITT-GT + VF) population. The mITT-GT + VF population is used to reduce the risk of bias that could occur due to either discordant HCV genotype or irrelevant failures unrelated to study drug. The mITT-GT + VF population includes all subjects who receive at least 1 dose of study drug (with imputation as described in Section 6.3) but excludes the subjects who are not of HCV genotype 1 infection and the subjects who were categorized as "prematurely discontinued study drug with no on-treatment virologic failure" and "missing follow-up data in the PT Period."

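### The missing = failure rule for SVR12 is carried into the primary outcome contrast, so a death before the SVR12 window can only be a non-SVR12 death, and no planned analysis checks this

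*SAP*

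**What the plan says.** **Exposure.** SAP 6.3 fills a missing HCV RNA value in steps: flanking values, then a value after the window, then a local laboratory value. If nothing is found, "Subjects with missing HCV RNA data in the analysis window, after imputations, will be imputed as a failure". SAP 10.3 brings this into the primary analysis, where HCV RNA values and SVR12 "will be imputed as described in Section 6.3". SAP 6.3 also handles subjects who begin another HCV therapy: "The subject will be considered a failure for summaries of viral response at all time points after the start of the new HCV treatment".

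**Time and events.** Time to event in SAP 10.3 is "the number of days from the first day of study drug dosing" to the event, and events on or off study drug all count. Subjects with no event and no death are censored at the "last available assessment of clinical outcomes". SAP Table 3 sets the SVR12 window at Study Drug End Days 57 to 126.

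**Sensitivity analyses.** SAP 10.6 defines two modified populations. One drops early discontinuers without virologic failure and subjects with missing follow-up, in order to "reduce the risk of bias that could occur due to either discordant HCV genotype or irrelevant failures unrelated to study drug". Both are for the SVR12 percentage only. SAP 10.3 plans no landmark, time-dependent or exclusion analysis of the clinical outcomes.

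**Related text.** Protocol 5.4.1 provides a yearly survival contact, with consent, for subjects who leave the study. Protocol 5.3.2.1 limits the primary endpoint to events in the post-treatment period. Protocol 5.6.1 calls the analyses descriptive, whereas SAP 4.3, 4.4 and 10.3 specify tests.

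**The concern.** Missing = failure is conservative for a response rate. It is not conservative when response is the exposure and death is the outcome, because survival then decides which group a subject is in.

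A subject who dies before the window opens has no later value, so neither flanking nor back-filling can rescue the status, and the subject becomes non-SVR12. The death still counts because the clock started at first dose. An SVR12 subject, by contrast, must have survived long enough to give a sample. Baseline covariates in the Cox model do not repair this, since the group label itself depends on survival.

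All-cause death is one of the six listed primary outcomes, and the non-SVR12 group is small. One or two subjects placed there by rule can change the death result, and nothing planned would show that it rested on subjects whose response was never observed.

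**Working it through.** **1. The plan's own figure.** Inputs from SAP 4.3: N = 2,000, 4% non-SVR12, a 20% five-year composite rate, HR 0.25, up to 20% dropout. Two-sided alpha is 0.05 (SAP 4.4).
- Non-SVR12 subjects: 0.04 × 2,000 = 80. The SVR12 five-year rate is 1 − 0.8^0.25 = 5.4%.
- Expected events with exponential dropout: 14.4 (non-SVR12) + 93.5 (SVR12) = 107.9.
- Schoenfeld: √(107.9 × 0.04 × 0.96) × ln 4 − 1.96 = 2.82 − 1.96 = 0.86, which gives power of 80.6%. The stated figure of over 80% is reproduced.

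**2. When the window opens.** Study Drug End Day 57 is about 8 weeks after the last dose, so about week 20 from first dose on 12 weeks of treatment and about week 32 on 24 weeks.

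**3. How many early deaths.** The documents do not say. Protocol Table 2 shows one death among 770 + 401 + 509 + 208 + 172 = 2,060 actively treated Phase 3 subjects, with timing not given. That is about 1 per 2,000 (exact 95% CI 0.02 to 5.4). Means of 0.5, 1 and 2 are used as assumptions.

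**4. Effect on all-cause death when the truth is HR = 1.** Null mortality is set at 0.5% a year (assumed) and at 1.39% a year, from the 6.7% five-year figure in Protocol 3.0: −ln(0.933)/5. Expected deaths among the 80 without early deaths are about 1.7 and 4.7. The ratio (SVR12 to non-SVR12) is roughly d/(d + k), where d is the expected deaths and k the mean number of early deaths. At k = 1 this is 1.7/2.7 = 0.63 and 4.7/5.7 = 0.82.

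Simulated unadjusted two-sided log-rank test (2,000 subjects, 20% dropout, early deaths at weeks 1-24, several thousand runs per cell):

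| Mean early deaths | False-positive rate, death | d/(d + k) |
|---|---|---|
| 0 | about 4-5% | 1 |
| 0.5 | about 7-10% | 0.77-0.90 |
| 1 | about 10-17% | 0.63-0.82 |
| 2 | about 18-35% | 0.46-0.70 |

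Nearly all false rejections favour SVR12. A second set-up used a common 5.4% five-year event rate and took one third of the non-SVR12 group as unknown and lost at 0.4 years. It gave 4.7%, 8.7% and 21% with exactly 0, 1 and 2 early deaths (median ratio 1.06, 0.79, 0.60). With unknowns excluded and a landmark start, the rate was 3.7%.

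**5. Composite at the design effect.** One early death is added to about 14 expected non-SVR12 events. A large-sample Cox fit moves the HR only from 0.25 to 0.24.

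**6. Dilution the other way.** Suppose unknowns behave like SVR12 subjects and are followed with sound censoring. A true death HR of ln(0.933)/ln(0.856) = 0.45 then becomes 0.45-0.47 when unknowns are 10% of the non-SVR12 group (assumed). As a ceiling, the Phase 3 arms with stated N had 76 subjects without SVR12 and 50 virologic failures, so 26/76 = 34% were not virologic failures. That includes early discontinuers who had HCV RNA data.

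**7. Survival contacts.** The contact is documented for this study only. SAP 4.3 gives "TOPAZ-I (planned to enroll 1650 subjects) and TOPAZ II (planned to enroll 600 subjects", so it covers 600/2,250 = 26.7% of subjects. If contact-found deaths count but contacted survivors are censored at exit, the false-positive rate for death is 4-7% across the assumed unknown shares and consent rates.

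**The case against.** **The sized endpoint is hardly touched.** This stands. Power rests on the composite, which moves by 0.01. The concern is mainly all-cause death.

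**The early-death counts are not calibrated.** This stands. They rest on one Phase 3 death. They are also lower than the null mortality rates would imply: 2,000 × 24/52 × 0.5% to 1.39% is about 4.6 to 12.8 deaths in 24 weeks. That mismatch points to a larger problem, not a smaller one, but the percentages remain illustrations.

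**Protocol 5.6.1 plans no hypothesis testing, and the simulated test is the unadjusted log-rank.** Partly stands. The SAP does name tests, so the documents disagree, and the covariate-adjusted Cox model was not simulated. The shift in the hazard ratio needs no test to matter.

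**On Protocol 5.3.2.1, on-treatment deaths are not primary events.** True of that definition, but SAP 10.3 counts them. Deaths between the last dose and Day 57 would remain either way.

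**Subjects who leave can still have a value.** Correct. HCV RNA is taken at the post-treatment discontinuation visit, so someone who leaves from Day 57 and attends it is not unknown. A reader might infer that a third of non-SVR12 subjects will be unknown, or that most unknowns will have died. The documents give no figure for either.

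**The censoring gap may look like a serious bias.** The documents do not support that. Death is itself a clinical outcome, so a survival contact can naturally be read as an assessment of it. Large effects arise only if TOPAZ-I uses the same contact, and its protocol is not available here.

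**Conclusion.** The point holds on explicit text. SAP 10.3 lets an imputed failure define the exposure and counts deaths that occur before the exposure can be observed. All-cause death is biased in favour of SVR12, and no planned analysis of the clinical outcomes would show how much.

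The size depends on the number of early deaths. At a mean of one, a true ratio of 1 appears as about 0.63-0.82, with a false-positive rate of about 10-17%. This assumes about 80 non-SVR12 subjects and annual mortality of 0.5-1.39%.

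A reader might go further and infer that the power statement is wrong or that the composite result would be unreliable at the design effect. Neither follows: the power reproduces at 80.6% and the composite stays at 0.24-0.25. The censoring wording is an ambiguity with a small effect where the contact is documented. The change is worth making before the final lock, because a landmark analysis chosen after the deaths are seen would carry little weight.

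**What to change.** In SAP 10.3:

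1. Keep the planned analysis and add one pre-specified sensitivity analysis for all-cause death and the composite.
   - Compare SVR12 with documented non-response: on-treatment virologic failure, relapse, or an observed, back-filled or local HCV RNA value at or above LLOQ. A flanked value cannot show failure, since flanking under SAP 6.3 yields only undetectable or unquantifiable results.
   - Show subjects with no HCV RNA evidence either way as a separate unknown group.
   - Classify subjects who start new HCV treatment by the evidence before that start.
   - Start time at Study Drug End Day 126, or at the date of the later value if status was flanked or back-filled. List earlier deaths and events by group.
2. State that all-cause death is censored at the last date known alive from any source, including the Protocol 5.4.1 contacts. State that non-fatal outcomes and the composite are censored at the last full clinical-outcome assessment, with later contact-found deaths and contacted survivors treated alike.
3. Reconcile Protocol 5.3.2.1 (post-treatment events only) with SAP 10.3 (events from first dose).

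**Cost.** SAP wording and extra tables from data already collected. The same rule is needed for the pooled TOPAZ-I data. Some subjects leave the added contrast: at assumed unknown shares of 10-38% of the 80, about 8-30 of 2,000 (0.4-1.5%).

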7.1 Demographic and Baseline Characteristics

Demographics include age, weight, height and BMI as continuous variables, and sex, race, ethnicity, age category (< 55 years or ≥ 55 years] and [< 65 or ≥ 65 years]), birth year (< 1945 , 1945 to 1965, > 1965), country, and BMI category (< 30 kg/m² or ≥ 30 kg/m²).

Baseline characteristics will include: HCV genotype 1 subtype (1a, 1b, 1-other), IL28B genotype ([CC, CT, or TT] and [CC or non-CC]), prior treatment history (treatment-naïve [IFN-eligible, IFN-ineligible] or IFN-based treatment-experienced [null responder, partial responder, relapser, relapse/breakthrough, nonresponder, IFN or pegIFN intolerant]), baseline HCV RNA levels ([continuous {use log₁₀ HCV RNA}] and [$< 800,000$ IU/mL or

$\geq 800,000$ IU/mL]), baseline HOMA-IR (< 3 or ≥ 3 mU \times mmol/L²), baseline fibrosis stage (F0-1, F2, F3, or F4), baseline Child-Pugh score (non-cirrhotic, 5, 6, or > 6), baseline FibroTest score, baseline albumin (continuous), baseline albumin (< 35 or ≥ 35 g/L), baseline creatinine clearance (GFR by Cockcroft Gault) (Continuous; < 30 mL/min, $\geq 30 - 49$ mL/min, $\geq 50 - 89$ mL/min, or ≥ 90 mL/min), baseline GFR by MDRD (continuous; < 30 , $30 - 59$, $60 - 89$, ≥ 90 mL/min/1.73m²; < 60 mL/min/1.73m² or ≥ 60 mL/min/1.73m²), baseline platelet count (continuous; $< 90 \times 10^9/L$ or $\geq 90 \times 10^9/L$; $< 50 \times 10^9/L$ or $\geq 50 \times 10^9/L$; $< 100 \times 10^9/L$ or $\geq 100 \times 10^9/L$; and $< 150 \times 10^9/L$ or $\geq 150 \times 10^9/L$), tobacco (user, ex-user, or non-user) and alcohol (drinker, ex-drinker, or non-drinker) use status, history of diabetes, history of depression or bipolar disorder, history of bleeding disorders, AST to platelet ratio index (APRI) (continuous; ≤ 2.0 or > 2.0), and Fibrosis-4 score (FIB-4) (continuous; ≤ 3.25 or > 3.25).

Subjects' HCV genotype and subtype may be assessed based on the Inno-LiPA 2.0 Assay used by the Central lab, the ARUP Assay for Hepatitis C High-Resolution Genotype by the Central lab and/or from phylogenetic analysis of the full length NS3/4a, NS5A, and/or NS5B sequences performed by AbbVie. If the phylogenetic analysis is available it will be used to determine the subject's HCV genotype and subtype. If it is not available, then the ARUP assay result will be used to determine the subject's HCV genotype and subtype, if available. Finally, if neither the phylogenetic analysis result nor the ARUP assay results are available, then the Inno-LiPA assay results will be used to categorize the subject.

Subjects' baseline fibrosis stage will be assessed by investigator during the screening period and categorized as F0 – F1, F2, F3, or F4.

Baseline Child-Pugh score is determined by the Day 1 assessment of ascites and hepatic encephalopathy along with the baseline values of total bilirubin, serum albumin, and international normalized ratio (INR). The Child-Pugh score is the sum of the point assigned for each of the five observed findings as defined in [Table 7](#).

Table 7. Child-Pugh Classification of Severity of Cirrhosis

Parameter	Points Assigned for Observed Findings		
	1	2	3
Total bilirubin, µmol/L (mg/dL)	< 34.2 (< 2)	34.2 – 51.3 (2 – 3)	> 51.3 (> 3)
Serum albumin, g/L (g/dL)	> 35 (> 3.5)	28 – 35 (2.8 – 3.5)	< 28 (< 2.8)
INR	< 1.7	1.7 – 2.3	> 2.3
Ascites*	None	Slight	Moderate to severe
Hepatic encephalopathy**	None	Grade 1 or 2 (or suppressed with medication)	Grade 3 or 4 (or refractory)

* None.

Slight ascites = Ascites detectable only by ultrasound examination.

Moderate ascites = Ascites manifested by moderate symmetrical distension of the abdomen.

Severe ascites = Large or gross ascites with marked abdominal distension.

** Grade 0: normal consciousness, personality, neurological examination, electroencephalogram.

Grade 1: restless, sleep disturbed, irritable/agitated, tremor, impaired handwriting, 5 cps waves.

Grade 2: lethargic, time-disoriented, inappropriate behavior, asterixis, ataxia, slow triphasic waves.

Grade 3: somnolent, stuporous, place-disoriented, hyperactive reflexes, rigidity, slower waves.

Grade 4: unarousable coma, no personality/behavior, decerebrate, slow 2 to 3 cps delta activity.

Baseline APRI and FIB-4 are defined as the equations below. Subjects without baseline values of AST, platelet count or age will be excluded from the summary of APRI; subjects without baseline values of AST, ALT, platelet count, or age will be excluded from the summary of FIB-4.

$$\text{APRI} = \frac{\left[\frac{\text{AST Level (IU/L)}}{\text{AST (Upper Limit of Normal) (IU/L)}} \right]}{\text{Platelet Count (10}^9\text{/L)}} \times 100$$

$$\text{FIB-4} = \frac{\text{Age (years)} \times \text{AST Level (U/L)}}{\text{Platelet Count (10}^9\text{/L)} \times \sqrt{\text{ALT (U/L)}}} \times 100$$

Summary statistics (N, mean, median, standard deviation [SD], and range) will be generated for continuous variables (e.g., age and BMI) and the number and percentage of subjects will be presented for categorical variables (e.g., sex and race).

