10.5 Efficacy Subgroup Analysis

The analysis on SVR₁₂ status as described in Section 10.4 will be performed on the ITT-II population for the following subgroups (assessed at baseline), as appropriate:

- The presence of cirrhosis and subgenotype (GT1b without cirrhosis, GT1b with compensated cirrhosis, GT1 non-b without cirrhosis, and GT1 non-b with compensated cirrhosis);
- prior treatment history (treatment-naïve [IFN-eligible, IFN-ineligible] or IFN/RBV treatment-experienced [null responder, partial responder, relapser, relapse/breakthrough, nonresponder, IFN or pegIFN intolerant]);
- IL28B ([CC, CT, TT] and [CC or non-CC]);
- Sex (male or female);
- Age (< 55 or ≥ 55 years) and (< 65 or ≥ 65 years);
- Birth year (< 1945, 1945 to 1965, > 1965);
- Race (Black or Non-Black; Black will include any subject who marks 'Black or African American' for race on the Demographics eCRF);
- Ethnicity (Hispanic or Latino, Not Hispanic or Latino);
- BMI (< 30 or ≥ 30 kg/m²);

- Baseline HCV RNA levels ($< 800,000$ or $\geq 800,000$ IU/mL; below median or above or equal to median);
- Baseline GFR by Cockcroft Gault (< 50 or ≥ 50 mL/min);
- Baseline GFR by MDRD (< 30 , $30 - 59$, $60 - 89$, ≥ 90 mL/min/1.73 m²; < 60 or ≥ 60 mL/min/1.73 m²);
- Baseline HOMA-IR (< 3 or ≥ 3 mU \times mmol/L²);
- History of Depression or Bipolar Disorder (yes/no);
- History of Bleeding Disorders (yes/no);
- Baseline Child-Pugh score (< 5 , 5 , 6 , or > 6);
- Baseline fibrosis stage (F0-F1, F2, F3, or F4);
- APRI (≤ 2.0 or > 2.0);
- FIB-4 (≤ 3.25 or > 3.25);
- Any of APRI > 2.0 and FIB-4 > 3.25 , or neither.

For subjects with cirrhosis only:

- Baseline platelets ($< 50 \times 10^9/L$ or $\geq 50 \times 10^9/L$; $< 90 \times 10^9/L$ or $\geq 90 \times 10^9/L$; $< 100 \times 10^9/L$ or $\geq 100 \times 10^9/L$; $< 150 \times 10^9/L$ or $\geq 150 \times 10^9/L$);
- Baseline albumin (< 35 or ≥ 35 g/L);
- Platelets $< 90 \times 10^9/L$ or albumin ≥ 35 g/L, or neither of the two.

For GT1 non-b subjects with cirrhosis only:

- Treatment Duration (12 weeks or 24 weeks).

Each subgroup analysis will be performed if there are an adequate number of subjects within each subgroup. The two-sided 95% Wilson score confidence interval for a binomial proportion (percentage of subjects achieving SVR₁₂) will be produced if there are at least 10 subjects in the subgroup.

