In addition, stepwise logistic regression will be performed on both SVR₁₂ and virologic failure (on-treatment virologic failure or relapse) using subgroup variables described

above as predictors of response. Some variables will be treated as continuous to decrease the chance of separation or quasi-separation and some variables may be eliminated if missing for many subjects.

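### SAP 7.1 multiplies FIB-4 by 100 while SAP 7.1 and 10.5 split it at 3.25, so virtually every subject falls above the cut-off

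*SAP*

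**What the plan says.** SAP 7.1 states "Baseline APRI and FIB-4 are defined as the equations below" and prints two equations, both ending in × 100:

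- APRI = (AST / AST upper limit of normal) / platelets × 100
- FIB-4 = age × AST / (platelets × √ALT) × 100

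The FIB-4 cut-off of 3.25 is used three times. SAP 7.1 lists the baseline characteristic as "Fibrosis-4 score (FIB-4) (continuous; ≤ 3.25 or > 3.25". SAP 10.5 has an SVR12 subgroup with the same split, and a combined subgroup of APRI above 2.0 or FIB-4 above 3.25 against neither. Neither document gives another FIB-4 scale or cut-off.

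Two rules govern these subgroups: "Each subgroup analysis will be performed if there are an adequate number of subjects within each subgroup", and the Wilson interval "will be produced if there are at least 10 subjects in the subgroup". The subgroup variables are also candidate predictors in the stepwise logistic regressions of SAP 10.5, where "Some variables will be treated as continuous to decrease the chance of separation or quasi-separation". The Cox models of SAP 10.3 take in all the SAP 7.1 characteristics.

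For cirrhotic subjects only, SAP 10.5 also defines a subgroup as platelets < 90 × 10⁹/L or albumin ≥ 35 g/L, "or neither of the two".

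**The concern.** The FIB-4 formula and its cut-off are on different scales. The factor of 100 suits APRI with its 2.0 cut-off. Applied to FIB-4, it moves ordinary values into the tens and hundreds while the threshold stays at 3.25. If the equation is programmed as printed:

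- the binary baseline row shows nearly everyone above 3.25;
- the FIB-4 subgroup for SVR12 has nothing to compare;
- the combined subgroup loses what APRI would have contributed, because FIB-4 alone puts everyone in the positive group;
- the binary FIB-4 term is constant, or nearly so, in the stepwise and Cox models;
- reported FIB-4 values are 100 times the scale of their own threshold.

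The platelet/albumin subgroup is a separate and smaller query. It joins an unfavourable platelet value to a favourable albumin value, so it does not separate more advanced from less advanced cirrhosis.

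**Working it through.** **Step 1: what the printed formula requires.** Let R = age × AST / (platelets × √ALT). Printed FIB-4 is 100 × R, so FIB-4 ≤ 3.25 requires R ≤ 3.25 / 100 = 0.0325.

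**Step 2: worked profiles.** The minimum age of 18 comes from Protocol 5.2.1. The AST, ALT and platelet values are assumptions for illustration.

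| Age | AST | ALT | Platelets (10⁹/L) | R | 100 × R |
|---|---|---|---|---|---|
| 18 | 20 | 20 | 400 | 360 / (400 × 4.472) = 0.20 | 20.1 |
| 30 | 25 | 30 | 300 | 750 / (300 × 5.477) = 0.46 | 45.6 |
| 50 | 60 | 70 | 180 | 3000 / (180 × 8.367) = 1.99 | 199 |
| 60 | 90 | 80 | 90 | 5400 / (90 × 8.944) = 6.71 | 671 |

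Without the factor, 3.25 separates the last row from the first three. With it, all four are far above.

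**Step 3: platelets needed to reach 3.25 with the factor.** Platelets = age × AST / (0.0325 × √ALT).

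- Age 18, AST = ALT = 20: 360 / (0.0325 × 4.472) ≈ 2,480 × 10⁹/L.
- Age 50, AST = ALT = 40: 2000 / (0.0325 × 6.325) ≈ 9,730 × 10⁹/L.

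**Step 4: can anyone fall at or below 3.25?** I used an unweighted grid over age 18–80, AST 10–300, ALT 10–400 and platelets 25–450 (assumed ranges). With the factor, 2,766 of 12,827,072 points (0.02%) are at or below 3.25. An example is age 18, AST 10, ALT 400, platelets 450: R = 180 / (450 × 20) = 0.020, giving 2.0. Only such extreme AST/ALT combinations qualify.

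Three simulated populations of 2,000,000 subjects each give the same picture. They represent mild, middle and severe disease, with mean ages 45/55/58, median AST 35/55/80, median ALT 45/60/80 and mean platelets 240/190/140, all assumed. Without the factor, 1.9%, 22.9% and 60.3% exceed 3.25, which is about 11, 137 and 362 of 600. With the factor, all do. The positive side of the APRI/FIB-4 composite goes from 2.2%, 23.6% and 61.4% to 100%.

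**Step 5: APRI as a check.** With an assumed AST upper limit of 40, AST 50 with platelets 200 gives 50/40/200 × 100 ≈ 0.62, and AST 90 with platelets 90 gives 90/40/90 × 100 = 2.50. These fall on either side of 2.0, so the factor belongs in APRI.

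**Step 6: the platelet/albumin subgroup.**

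| Platelets | Albumin | As printed | If albumin were < 35 |
|---|---|---|---|
| < 90 | < 35 | either | either |
| < 90 | ≥ 35 | either | either |
| ≥ 90 | < 35 | neither | either |
| ≥ 90 | ≥ 35 | either | neither |

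As printed, the neither group consists only of subjects with low albumin. Subjects favourable on both are pooled with subjects unfavourable on both.

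For size, I took the 100 to 150 F4 subjects of SAP 4.2. I assumed 10% or 20% with low albumin and 15% or 30% with low platelets, either independent or with the overlap set at 60% of the smaller margin. That makes 16 scenarios.

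- Smallest neither group: 100 × (0.10 − 0.06) = 4.
- Largest neither group: 150 × 0.20 × 0.85 = 25.5.
- It is below the 10-subject minimum for a confidence interval in 7 of the 16.
- The either group contains the 56–81% favourable on both together with the 1.5–12% unfavourable on both.

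**The case against.** The main point rests on one symbol. The × 100 appears once for FIB-4, directly below an APRI equation that ends the same way, and the text was read from the PDF by software, so it could be a reading error. That cannot be excluded without the page, and the point stays conditional on that check. Two things favour a faithful reading. The two equations keep different unit labels (IU/L and U/L). SAP 7.1 also drops subjects with missing age from the APRI summary although age is not in the APRI equation, which suggests text was carried between the two definitions.

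The consequences are also limited, and this stands. The subgroups are exploratory, run only where appropriate, and have no multiplicity adjustment. Continuous FIB-4 is only rescaled. Fibrosis stage, cirrhosis, Child-Pugh score, APRI, platelets and albumin already cover severity. At the plan's assumed 4% non-response, 600 subjects yield about 24 failures (0.04 × 600), so even a corrected FIB-4 split would be descriptive. A table with everyone above 3.25 would probably be noticed at a dry run.

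The simulated prevalences come from assumed inputs. They show that the corrected split could lie almost anywhere, but not where it will lie. The conclusion needs only Steps 1 to 3.

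The platelet/albumin rule can be computed as written, and nothing in the SAP says that both conditions must be unfavourable. That item is rightly no more than a query.

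**Conclusion.** The mismatch is real in the text as it stands: the SAP's definition of FIB-4 and its cut-off of 3.25 cannot both be used. Programmed as printed, the lower category is effectively empty rather than strictly impossible. One baseline row, one SVR12 subgroup, the APRI/FIB-4 composite and the binary FIB-4 model term then carry essentially no information about FIB-4. This rests on ordinary AST, ALT and platelet values and on the printed page carrying the factor.

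Eligibility, fibrosis staging, treatment assignment, sample size, power, the SVR12 rate and the log-rank comparison do not use FIB-4. In the Cox model a constant binary term drops out without changing the SVR12 estimate, and continuous FIB-4 still adjusts in the same way. The error is worth correcting because it sits in an operative definition, but it does not threaten the primary analysis.

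On platelets and albumin, the directions do differ as printed. The SAP's Child-Pugh table treats albumin above 35 g/L as the best category, and the APRI/FIB-4 composite combines two unfavourable conditions. A reversed sign is therefore plausible, but the intent is inferred and must be confirmed.

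**What to change.** 1. Compare the FIB-4 equation in SAP 7.1 with the source page and the programming specification.
2. If the factor is there, delete × 100 from the FIB-4 equation only. Keep it in APRI, and keep 3.25 throughout. This is the smallest edit, since the cut-off appears three times and the factor once.
3. Confirm the intended direction of the platelet/albumin subgroup in SAP 10.5. If both conditions are meant to be unfavourable, define it as platelets < 90 × 10⁹/L or albumin < 35 g/L, against neither. If the printed direction is intended, add a sentence giving the reason.

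The cost is one factor and at most one inequality sign. No new data are needed, and the primary comparison of SVR12 groups does not change.
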